University of Virginia

Is adrenal insufficiency under- diagnosed in hospitalized cirrhosis patients?

NCT03368066

PI: [name]
11-20-2017

PROTOCOL

Background

1. Provide the scientific background, rationale and relevance of this project.

Answer/Response:

Cirrhosis is known to cause various end-organ dysfunction, most notably the hepatorenal and hepatopulmonary syndromes. However, the increased recognition of adrenal insufficiency in cirrhotic patients has led to postulation about the presence of a so-called “heptoadrenal syndrome¹.” While originally this syndrome was recognized in cirrhotic patients with sepsis and shock states^{1,2}, further investigation has also identified adrenal insufficiency in cirrhotic patients with variceal bleeding³ as well as stable patients⁴. Although there is controversy about the best diagnostic test to assess adrenal insufficiency in cirrhotic patients^{5,6}, it is well established that cirrhotic patients with adrenal insufficiency have increased mortality, particularly as they become more decompensated⁷.

In addition to this endocrinological complication, cirrhosis also has a profound effect on a patient’s hematologic parameters. In a study of rheologic properties of 38 patients (18 cirrhotic – mostly of cryptogenic origin, 20 control), cirrhotic patients were noted to have increased erythrocyte rigidity and decreased plasma and blood viscosity⁸. The authors argued that their findings were related to a deficiency of high-density lipoprotein (HDL), although the correlation was admittedly weak in their study. A follow-up study by the same authors also confirmed an increase in erythrocyte rigidity in patients with alcoholic and post-hepatic cirrhosis; importantly, they noted the prior association between alcoholic liver disease and development of macrocytosis as a function of lecithin-cholesterol acetyltransferase (LCAT) enzyme deficiency⁹. This enzyme is responsible for esterification of cholesterol and subsequent incorporation into normal red cell membranes. Interestingly, its deficiency is directly manifested as an altered free cholesterol to phospholipid ratio¹⁰, with the increased cholesterol fraction causing the membrane rigidity previously described.

Another abnormality well documented in cirrhotic patients, more frequently in patients with advanced disease, is spur cell anemia. Although first described in alcoholic cirrhosis, it is seen in all etiologies and is a poor prognostic marker. A spur cell burden of $\geq 5\%$ was found to be associated with a 67% 90-day mortality rate in a recent study¹¹. Furthermore, patients with spur cell anemia have decreased red blood cell (RBC) lifespan and are transfusion resistant as transfused RBCs quickly acquire the pathologic morphology. Spur cells are thought to occur secondary to red cell membrane abnormalities secondary to altered cholesterol composition, similar to the abnormal erythrocyte rigidity rheologic property described above. Interestingly, the lecithin-cholesterol acetyltransferase enzyme has been investigated as a potential key factor in spur cell anemia. A 1972 study by Cooper et al¹² measured LCAT enzyme activity by way of a surrogate method involving change in serum free cholesterol after 6-hour incubation. Lower levels of LCAT were found in patients with spur cells compared to normal controls; however, there was only a weak association with red cell lipid content.

Furthermore, platelet dysfunction in cirrhosis has also been tied to lipid abnormalities. A review of dyslipidemia in liver disease by Miller noted that platelets, similar to erythrocytes, have an imbalanced cholesterol to phospholipid ratio and associated impaired aggregation¹³. Thus, the deficient primary hemostasis noted in cirrhotic patients may not be just a function of

thrombocytopenia itself but also an intrinsic abnormality of platelet function related to a disruption in normal cholesterol pathways.

It has been demonstrated that LCAT is a key enzyme for many homeostatic functions within the human body and its deficient production in cirrhosis appears to correlate with various hematologic abnormalities. However, it may very well also play an important role in adrenal steroidogenesis and help explain the so called "hepatoadrenal" syndrome that has begun to permeate through the literature. More importantly, however, is that cholesterol esterification levels, a surrogate marker of LCAT enzymatic activity, are directly associated with mortality and thus can serve as a prognostic indicator. A recent study by Kaiser et al.¹⁴ found that the cholesterol esterification fraction was more accurate than INR for estimation of liver synthetic capability and both 3-month and 1-year mortality. Thus, if one can quantify this deficiency in cirrhotic patients and demonstrate association with several related pathologic conditions, it may soon become a useful biomarker to direct treatment and more reliably predict mortality.

Objectives/Hypothesis

Answer/Response:

The hepatoadrenal syndrome has been well described in the literature and is known to be associated with poorer outcomes in both stable and critically ill cirrhotic patients. In chronic liver disease, adrenal (and more specifically cortisol) insufficiency is thought to be a byproduct of altered lipid metabolism that results in decreased HDL production and thus decreased delivery of cholesterol to the adrenal for subsequent corticosteroid production. Studies to date have implicated lecithin-cholesterol acetyltransferase (LCAT) as the key enzyme which is deficient in some cirrhotic patients, leading to an impaired ability to esterify cholesterol and thus a loss of normal cellular functioning and membrane stability. We seek to quantify this LCAT deficiency in a cohort of cirrhotic patients and demonstrate its association with various abnormal physiologies associated with chronic liver disease, including spur cell anemia, low HDL levels, and adrenal insufficiency.

Study Design: Biomedical

1. Will controls be used?

Answer/Response: No a priori controls (i.e. we will not be including patients without cirrhosis in our study). We will compare cirrhotic patients with and without adrenal insufficiency.

► **IF YES, explain the kind of controls to be used.**

Answer/Response: N/A

2. What is the study design?

Answer/Response: prospective cohort study

3. Does the study involve a placebo?

Answer/Response: No

► **IF YES, provide a justification for the use of a placebo**

Answer/Response: N/A

Human Participants

Ages: 18-100

Sex: Men and women

Race: All

Subjects- see below

1. Provide target # of subjects (at all sites) needed to complete protocol.

Answer/Response: 100

2. Describe expected rate of screen failure/ dropouts/withdrawals from all sites.

Answer/Response: 20

3. How many subjects will be enrolled at all sites?

Answer/Response: 120

4. How many subjects will sign a consent form under this UVa protocol?

Answer/Response: 120

Inclusion/Exclusion Criteria

1. List the criteria for inclusion

Answer/Response:

- age \geq 18 years,
- diagnosis of cirrhosis,
- admission to hospital

2. List the criteria for exclusion

Answer/Response:

- age $<$ 18 years,
- prior enrollment in study (i.e. readmission),
- prisoner,
- prednisone or hydrocortisone use in the past 24 hours,
- pregnancy

3. List any restrictions on use of other drugs or treatments.

Answer/Response: None

Statistical Considerations

1. Is stratification/randomization involved?

Answer/Response: No

► IF YES, describe the stratification/ randomization scheme.

Answer/Response: N/A

► IF YES, who will generate the randomization scheme?

 Sponsor

UVa Statistician. Answer/Response:
UVa Investigational Drug Service (IDS)
Other: Answer/Response:

2. What are the statistical considerations for the protocol?

Answer/Response:

Subjects will be classified as adrenally sufficient or insufficient on the basis of standard-dose cortisol stimulation test. Variables of interest for comparison between the groups include MELD score, Child-Turcotte-Pugh (CTP) classification, high-density lipoprotein (HDL) levels, presence of spur cell anemia, serum cholesterol ester percentage (surrogate for LCAT enzymatic activity), cortisol binding globulin levels, and free cortisol levels. Student's t-test and Chi Square tests will be utilized to determine significance; a p-value <0.05 will be used as our threshold for significance. If multiple factors are found to be significantly different in a univariate fashion between classification groups, a multivariate logistic regression analysis will be performed for adjusted analysis. We will also seek to define any correlations between variables. Furthermore, we will assess correlation between MELD score and serum cholesterol ester percentage, spur cell anemia, HDL levels, cortisol binding globulin levels, and free cortisol levels; similar correlate analysis will be done using CTP classification instead of MELD score.

Prevalence of adrenal insufficiency (AI) in cirrhosis varies widely based on several factors, including severity of liver disease (i.e. MELD score or CTP classification) and the testing modality used to assess for AI. Given that admitted patients to UVA are typically CTP B or C, we expect the incidence to be about 33%. Thus, 120 patients recruited should be sufficient to provide a statistical difference in our outcome measures of interest, assuming a 20% dropout rate to lead to 100 patients completing study protocol.

3. Provide a justification for the sample size used in this protocol.

Answer/Response:

Given that admitted patients to UVA are typically CTP B or C, we expect the incidence of adrenal insufficiency to be about 33%. We feel 100 patients would be adequate to complete a pilot study to test for correlation between adrenal insufficiency, low serum cholesterol ester percentage, and spur cell anemia. There is no current literature upon which to do a formal power calculation (although low levels of cholesterol esterification is a well-established near-universal metabolic finding in cirrhotic patients), but this sample size would allow for adequate size comparator groups and decrease the likelihood of a Type II statistical error.

4. What is your plan for primary variable analysis?

Answer/Response:

Our primary outcome of interest is comparing prevalence of cholesterol esterification deficiency and spur cell anemia in cirrhotic patients with and without adrenal insufficiency.

5. What is your plan for secondary variable analysis?

Answer/Response:

- Demonstrate association between deficiency in cholesterol esterification and presence of spur cell anemia

- Demonstrate association between deficiency in cholesterol esterification and low HDL levels
- Correlate higher MELD score with presence of adrenal insufficiency
- Correlate higher MELD score with presence of spur cell anemia
- Correlate higher MELD score with lower HDL levels
- Correlate higher MELD score with deficiency in cholesterol esterification
- Correlate higher CTP classification with presence of adrenal insufficiency
- Correlate higher CTP classification with presence of spur cell anemia
- Correlate higher CTP classification with lower HDL levels
- Correlate higher CTP classification with deficiency in cholesterol esterification
- Correlate lower cortisol binding globulin levels with higher MELD score and CTP classification
- Correlate lower cortisol binding globulin levels with adrenal insufficiency
- Correlate lower free cortisol levels with higher MELD score and CTP classification
- Correlate lower free cortisol levels with adrenal insufficiency
- Multivariate logistic regression if several variables are found to be significant

6. Have you been working with a statistician in designing this protocol?

Answer/Response: No

IF YES, what is their name?

Answer/Response: N/A

7. Will data from multiple sites be combined during analysis?

Answer/Response: No

7(a). Does the study involve randomization?

Answer/Response: No

IF YES, will randomization be done at each site or among sites?

Answer/Response: N/A

7(b). Has the sample size calculation considered the variation among sites?

Answer/Response: N/A

7(c). When combining the data from multiple sites to assess the study results, is the effect of the treatment to be tested (or the association to be tested) assumed to be the same across sites or vary among sites? What is the modelling strategy?

Answer/Response: N/A

7(d). Is there a common protocol used in all sites?

Answer/Response: N/A

IF NO, how will differences among sites, such as those related to the implementation, inclusion criteria, patient characteristics, or other sites characteristics, be considered to assess the study results?

Answer/Response: N/A

Study Procedures-Biomedical Research

1. What will be done in this protocol?

Answer/Response:

Hospitalized cirrhotic patients at UVA that meet study eligibility criteria will be approached by a member of the study team to obtain consent for participation. If a patient agrees to become a study subject, women of childbearing potential will be administered a urine pregnancy test to exclude pregnancy. Eligible subjects will have an approximate total of 35ml of blood drawn by the inpatient phlebotomy team. Lab tests to be performed include: peripheral blood smear, lipid panel, free cortisol, cortisol binding globulin, serum cholesterol esters (surrogate for LCAT enzyme activity), and a standard-dose cortisol stimulation test. The latter involves blood drawn with the initial collection, administration of an intravenous 250mcg dose of synthetic ACTH by the patient's nurse, and then repeat small-volume (2 teaspoons) blood draws at 30 minutes and 60 minutes later.

The interventions listed above have the potential to identify subjects with adrenal insufficiency, which may be beneficial to their long-term care. Early identification of adrenal insufficiency may lead to earlier corticosteroid administration in critical illness or GI bleeding, thus improving morbidity and mortality. Otherwise, the blood draws themselves pose minimal risk given that it is a routine procedure done during hospitalization, often on a daily or even more frequent basis. Very small risks of bleeding, bruising, or infection do exist.

Most patients tolerate intravenous ACTH as part of the cortisol stimulation test, however known reactions include nausea, diaphoresis, dizziness, pruritus, palpitations, and facial flushing. All patients will be monitored and these side effects, if present, typically resolve within a few hours. Any patients identified as having adrenal insufficiency will be reported to the primary hepatology team caring for the patient to determine whether or not endocrinology consult and/or treatment should be considered.

2. If this protocol involves study treatment, explain how a subject will be transitioned from study treatment when they have completed their participation in the study.

Answer/Response: N/A

Subject Compliance with Study Procedures

1. Explain how the study team will monitor the subject for compliance with the study procedures.

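### No recording of sepsis, shock or bleeding is planned, so the plan cannot show whether acute illness contributes to the comparison of patients with and without adrenal insufficiency

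*Combined protocol and SAP*

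**What the plan says.** All places are in the combined protocol and SAP.

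- **Background.** AI in cirrhosis is introduced through acute illness: "originally this syndrome was recognized in cirrhotic patients with sepsis and shock states", and "further investigation has also identified adrenal insufficiency in cirrhotic patients with variceal bleeding". The second sentence adds stable patients.
- **Inclusion/Exclusion Criteria.** Besides adult age and a cirrhosis diagnosis, the only entry condition is "admission to hospital". The one exclusion that touches acute illness is "prednisone or hydrocortisone use in the past 24 hours". The others are age under 18, earlier enrolment, prisoner status and pregnancy.
- **Statistical Considerations, item 2.** Groups are formed by one test: "Subjects will be classified as adrenally sufficient or insufficient on the basis of standard-dose cortisol stimulation test". The list of variables begins "Variables of interest for comparison between the groups include MELD score, Child-Turcotte-Pugh (CTP) classification" and continues with HDL, spur cell anemia, cholesterol ester percentage, cortisol binding globulin and free cortisol. A logistic regression follows only if several of these differ between the groups in univariate tests.
- **Statistical Considerations, items 4 and 5.** The primary outcome compares how often esterification deficiency and spur cell anemia occur with and without AI. No secondary analysis involves acute illness.
- **Study Procedures, item 1.** The data items are laboratory tests and the stimulation test. Critical illness and GI bleeding appear again, but only as settings where detecting AI might help care.

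**The concern.** The study is an observational cohort, and its objective is to show that LCAT deficiency is associated with AI. A factor related both to AI and to esterification or spur cells would produce such an association even if LCAT and adrenal function were unconnected. The authors themselves name sepsis, shock and bleeding as settings of AI, and the eligibility criteria let these patients in beside stable ones. Because no acute-illness item is listed, the conditional regression as written cannot adjust for it. A reader of the results could not tell whether the AI group simply held more septic, shocked or bleeding patients.

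**Working it through.** **No figure of the plan's own to reproduce.** The plan states no power, effect size or outcome rate for this comparison. It gives 100 completers and about 33% AI, hence about 33 against 67 patients, and a threshold of p < 0.05 (two-sided assumed).

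**Assumed inputs (not in the documents).** 30% of patients are acutely ill; AI occurs in 50–60% of them; their ester percentage is 0.5–0.8 SD lower. A milder case uses 45% and 0.3 SD. Within the acutely ill, and within the rest, AI and ester percentage are unrelated, so every rejection is a false positive.

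**Step 1: imbalance between groups.** With AI in 55% of the acutely ill:
- AI in the others = (0.33 − 0.30 × 0.55) / 0.70 = 0.24
- P(acute | AI) = 0.30 × 0.55 / 0.33 = 0.50
- P(acute | no AI) = 0.30 × 0.45 / 0.67 = 0.20

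**Step 2: spurious difference in ester percentage.** Effect × [P(acute | AI) − P(acute | no AI)] = 0.8 × (0.50 − 0.20) = 0.24 SD.

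**Step 3: the stated binary outcome.** The plan gives no cut-off for deficiency, so two cases are shown. If a share q of the patients without acute illness is deficient, the share in the acutely ill is Φ(Φ⁻¹(q) + effect).
- q = 38%: Φ(−0.305 + 0.8) = 69%; spurious difference (0.69 − 0.38) × 0.30 = 9 percentage points.
- q = 84%: Φ(0.994 + 0.8) = 96%; spurious difference (0.96 − 0.84) × 0.30 = 4 percentage points.

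The second case matters because item 3 of Statistical Considerations describes low esterification as almost universal in cirrhosis. A near-ceiling outcome leaves little room for a spurious gap.

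**Step 4: false-positive rates.** 20,000 simulated trials of 100 patients per row; t-test on ester percentage, linear model adding one acute-illness indicator, and uncorrected chi-square on deficiency.

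| AI in acutely ill | Ester deficit | Spurious difference | t-test | Linear model with indicator | Chi-square, q = 38% | Chi-square, q = 84% |
|---|---|---|---|---|---|---|
| 60% | 0.8 SD | 0.29 SD | 26% | 5% | 19% | 8% |
| 55% | 0.8 SD | 0.24 SD | 18% | 5% | 14% | 6% |
| 55% | 0.5 SD | 0.15 SD | 11% | 5% | 9% | 6% |
| 50% | 0.5 SD | 0.12 SD | 8% | 5% | 7% | 5% |
| 45% | 0.3 SD | 0.05 SD | 6% | 5% | 6% | 5% |
| 55% | none | 0 | 5% | 5% | 5% | 5% |

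**Step 5: a wider range for any binary outcome.** Spur cell anemia has no stated prevalence. Take 33 against 67 patients, 20–60% acutely ill, an odds ratio of 2–6 between acute illness and AI, and the outcome in 30% of those without acute illness. A normal approximation gives a false-positive rate of about 6–13% if the outcome occurs in 50% of the acutely ill, about 8–35% if it occurs in 70%, and 5% if it stays at 30%.

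**The case against.** The strongest objection is that half of the confounding path is missing from the documents. Nothing in them links sepsis, shock or bleeding to ester percentage or spur cells, and without that link the false-positive rate is 5%. This stands, and it makes the point conditional. The AI half is also softer than it looks. A reader might infer from the Background that AI is more frequent in the acutely ill, but the text says only that it was recognized in those settings, and it names stable patients too.

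MELD and CTP may carry part of acute severity. If a severity score correlated 0.5–0.8 with a latent measure of acute illness (assumed), adjusting for it would bring the 18–19% setting down to about 10–15%. So it would be wrong to say that these scores capture none of it. The mitigation is partial, however, and it applies only if the univariate screen triggers the regression.

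The 24-hour steroid exclusion may remove some acutely ill patients, but not those who have not received these drugs. The variable list is introduced as non-exhaustive, so the accurate statement is that no recording is planned.

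The study is described as a pilot and seeks association, and mixed admissions suit its title question. That argues for leaving eligibility alone. It does not remove the need to describe the case mix, since the plan still tests at p < 0.05.

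Finally, adjustment is not neutral. Shock could be a consequence of AI, and conditioning on it could itself distort the association. This stands and shapes the fix.

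**Conclusion.** The point holds as a conditional one, and the change is worth making. Acute illness is not an entry restriction, a planned data item, a compared variable or an adjustment variable, although the Background ties AI to it. If it is also related to the outcome, the comparison can reflect acute illness as well as, or instead of, an LCAT-adrenal link. Under the main assumptions the false-positive rate for esterification deficiency is about 7–19% at 38% deficiency and about 5–8% at 84%. For a t-test on ester percentage it is about 8–26%. In the milder setting it is about 5–6%. Only the 100 patients and the 33% come from the plan.

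Three stronger readings are not supported:
- That the comparison is in fact confounded. The documents do not give the link to the outcome.
- That the t-test range is the error rate for the primary outcome. That outcome is a prevalence, and its rate depends on an undefined cut-off.
- That the omission cannot be repaired later. Acute status may be recoverable from the medical record, which the protocol mentions only for tracking compliance. Recording it at the time of the test, with the analysis fixed in advance, is still better than choosing an adjustment after the results are seen.

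**What to change.** 1. Record from the medical record, as three separate yes/no items, sepsis, shock and GI bleeding at the time of the stimulation test. Report each by AI group.
2. Keep the unadjusted primary comparison as it is.
3. Pre-specify beside it one analysis of the primary outcomes adjusted for a single indicator of any of the three, run regardless of the univariate screen, and one sensitivity analysis in patients with none of them.
4. State in the plan that shock may be a consequence of AI, so that the adjusted result is read beside the unadjusted one and does not replace it.

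The cost is a few chart fields per patient, one degree of freedom (affordable with about 33 AI cases), and lower precision in the restricted analysis. Eligibility and study procedures for patients do not change.

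### Minor, cheap improvement: use Welch's rather than Student's t-test for the continuous comparisons between adrenal-insufficiency groups of about 33 and 67

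*Combined protocol and SAP*

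**What the plan says.** Statistical Considerations, item 2, sorts patients into adrenally sufficient and insufficient groups by the standard-dose cortisol stimulation test and compares them on a list of measures: "Variables of interest for comparison between the groups include MELD score, Child-Turcotte-Pugh (CTP) classification, high-density lipoprotein (HDL) levels", followed by spur cell anemia, cholesterol ester percentage, cortisol binding globulin and free cortisol. On method it says only that "Student's t-test and Chi Square tests will be utilized to determine significance" and that "a p-value <0.05 will be used as our threshold for significance". If several factors reach significance singly, a multivariable logistic regression follows.

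On group sizes, the same item says "we expect the incidence to be about 33" per cent, and plans for 100 patients to complete. It also warns: "Prevalence of adrenal insufficiency (AI) in cirrhosis varies widely based on several factors". Item 3 adds: "There is no current literature upon which to do a formal power calculation".

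Item 4 gives the primary outcome as "comparing prevalence of cholesterol esterification deficiency and spur cell anemia in cirrhotic patients with and without adrenal insufficiency". Item 5 lists secondary aims, several of which correlate MELD score, cortisol binding globulin or free cortisol with AI. Neither these items nor any other part of the document mentions unequal variances, a variance check, a transformation or a rank test. Item 6 records that no statistician took part in the design.

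**The concern.** Student's t-test estimates one common variance from both groups, weighted by their sizes. When the groups are about equal in size, unequal SDs do little harm. When one group is twice the other, the pooled estimate is dominated by the larger group. If the smaller AI group is the more variable, the standard error is too small and p-values are too small. If the AI group is the less variable, p-values are too large and power is lost.

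The groups here are not randomised. They are formed by a cortisol response and then compared on cortisol-related and liver-related measures, so nothing in the design makes equal spread a safe default. The same p-values also decide whether the adjusted analysis is run.

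**Working it through.** **Inputs from the document.** AI share about 33% and 100 completers (item 2); significance threshold 0.05 (item 2). The group sizes are not printed: 0.33 × 100 = 33 and 100 − 33 = 67.

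**Assumptions.** Two-sided test, since sidedness is not stated; normal data; SD ratio k (AI/non-AI) from 0.5 to 2, since no SDs are given; differences in means expressed in non-AI SDs.

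**The plan's own figure.** The sample size of 100 cannot be reproduced, because no effect, SD or power is stated. Taking 20% off the 120 recruited would leave 120 × 0.80 = 96, or about 32 vs 64. The error rates there are nearly the same (1.7% at k = 0.5, 11.0% at k = 2), so this does not affect the point.

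**Large-sample formula.** With the non-AI SD set to 1:
- variance the pooled test uses: P = [(33k² + 67)/100] × (1/33 + 1/67)
- true variance of the difference in means: T = k²/33 + 1/67
- true type I error = 2 × [1 − Φ(1.96 × √(P/T))]

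Worked for k = 2: P = 1.99 × 0.04523 = 0.0900; T = 0.1212 + 0.0149 = 0.1361; √(P/T) = 0.813; 1.96 × 0.813 = 1.594; error = 11.1%.

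Worked for k = 0.5: P = 0.7525 × 0.04523 = 0.0340; T = 0.0076 + 0.0149 = 0.0225; √(P/T) = 1.230; 1.96 × 1.230 = 2.411; error = 1.6%.

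**All ratios, 33 vs 67, nominal 5%.** The simulated columns come from 500,000 trials per row; other runs differ by 0.1 to 0.2 points.

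| SD ratio AI/non-AI | Student, formula | Student, simulated | Welch, simulated |
|---|---|---|---|
| 0.5 | 1.6% | 1.7% | 5.0% |
| 0.67 | 2.5% | 2.6% | 5.0% |
| 0.8 | 3.5% | 3.4% | 4.9% |
| 1.0 | 5.0% | 4.9% | 5.0% |
| 1.25 | 6.9% | 6.9% | 5.0% |
| 1.5 | 8.6% | 8.6% | 5.0% |
| 2.0 | 11.1% | 11.1% | 5.0% |

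**Is the imbalance the cause?** Yes. At 50 vs 50, Student's test stays at 4.9% to 5.1% over the same ratios. At 20 vs 80, which is possible because the document says prevalence varies widely, it runs from 0.4% (k = 0.5) to 18.1% (k = 2).

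**Power.** At k = 0.5 and a difference of 0.45 non-AI SDs, power is 71% with Student's test and 84% with Welch's. With equal SDs, the cost of Welch is small:

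| Difference (SDs) | Student | Welch |
|---|---|---|
| 0.4 | 46.1% | 45.7% |
| 0.5 | 64.3% | 63.8% |
| 0.6 | 79.8% | 79.4% |
| 0.7 | 90.3% | 89.9% |

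**Skewed data.** With lognormal values (log-SD 0.8) rescaled to SD ratios of 1.5 and 2, type I error is 8.6% and 11.9% with Student's test, and 6.6% and 7.5% with Welch's.

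**The correlation items.** For a binary group and a continuous measure, the usual test of a Pearson correlation r is t = r√(n − 2)/√(1 − r²). This is algebraically the pooled t statistic. Correlating MELD, cortisol binding globulin or free cortisol with AI in that way would bring the same assumption back under item 5.

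**The case against.** The best reply is that a false-positive argument needs equal means together with unequal SDs. If a measure is unrelated to AI, its whole distribution is the same in both groups, spread included, and the pooled test holds its 5%. This stands in part. Forming groups by a cortisol result makes unequal spread easiest to imagine for free cortisol and cortisol binding globulin, and for free cortisol equal means are themselves doubtful. The inflated error rates are therefore a less natural description of this study than the loss of power, which does not depend on equal means.

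Three other replies also stand:
- No SDs are given, and for ratios near 1 the error is small. The 11% figure needs the AI group to have four times the variance.
- The study is described as a pilot, and "Student's" is often used loosely. If the team meant Welch's test, the edit only removes an ambiguity.
- Welch's test does not cure skewness.

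A reader might go further and infer that the primary result is at risk. The document does not support that: item 4 words the primary outcome as a comparison of prevalences, to which the chi-square test applies. The t-test would reach the primary question only if ester percentage were compared as a mean. A reader might also infer that the planned p-values will be materially wrong. Without SDs this cannot be said; the document shows only that the named test relies on an assumption it gives no reason to make.

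None of these replies shows that the pooled test is the better choice.

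**Conclusion.** The point holds as a minor improvement. For two groups of about 33 and 67, the named test keeps its error rate only if the SDs are similar, and Welch's test does so without that condition when data are roughly normal. On assumed SD ratios, the departure from 5% is slight near equality (about 3.5% to 6.9% for ratios of 0.8 to 1.25) and marked at the extremes (about 1.7% to 11.2% for 0.5 to 2). The power loss can reach 13 points (84% − 71%) at a ratio of 0.5 and a difference of 0.45.

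The conclusion rests on reading "Student's" in its standard sense, on a 1:2 split inferred from the expected AI share, and on SD ratios that the document neither gives nor rules out. It covers the secondary mean comparisons and the screen that leads to the regression, not the primary prevalence comparison.

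**What to change.** In item 2, replace Student's t-test with Welch's (unequal-variance) t-test for every continuous AI versus non-AI comparison: MELD, HDL, cholesterol ester percentage, cortisol binding globulin and free cortisol. Report each mean difference with its Welch 95% confidence interval.

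In item 5, state that the aims relating MELD, cortisol binding globulin or free cortisol to AI will use the same test, so that an ordinary correlation does not reintroduce the pooled variance. Add that strongly skewed assay values may be log-transformed before comparison.

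The cost is a sentence or two of text and 0.3 to 0.5 percentage points of power if the SDs are equal. No extra patients, samples or procedures are needed.
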